8. BACKGROUND AND RATIONALE

Irritable bowel syndrome (IBS) is a common, painful, and often disabling gastrointestinal (GI) disorder characterized by abdominal pain/discomfort associated with alterations in bowel habits. As a functional disorder, IBS lacks a reliable biomarker and is therefore best understood from a biopsychosocial perspective ³⁷. The bowel abnormalities may manifest in constipation, diarrhea, or both in alteration. IBS is estimated to afflict 6-14 million of the adult population in the U.S. ³⁸. Even though most IBS participants do not seek medical attention, IBS remains one of the most common GI disorders and more common than such important disease as diabetes, asthma, ischemic heart disease, and hypertension ³⁹⁻⁴⁰. IBS accounts for 40% of the referrals made to gastroenterologists (GE) and is the 7th leading diagnosis made by primary care physicians in the U.S. ⁴⁰. IBS is also costly in terms of medical treatments and diagnostic procedures ⁴¹, time lost from work ⁴², and non-monetary costs such as diminished quality of life ⁴²⁻⁴³ and activity limitations ⁴⁴. A conservative estimate of the combined social and economics costs of IBS is \$20 billion annually ⁴⁵⁻⁴⁶. It is believed that the lack of a satisfactory medical treatment partly drives these costs ⁴⁷.

There is therefore a demand among primary care physicians, gastroenterologists, health insurance providers, participants ⁴⁸⁻⁴⁹ and their employers for effective self-management treatments for those who are most burdened by IBS, derive limited relief from conventional medical options, and consume a disproportionate share of scarce health care resources.

Our previous research has provided a strong, empirical foundation for performing a randomized clinical trial of the effects of MC-CBT, relative to those evoked by S-CBT and an appropriate attention-control (psychological placebo) condition, on participants' reports of overall improvement as well as improvement in clinical symptoms, psychological distress, and related measures of quality of life and health care usage. This clinical trial also will address five critical aims that have not been examined in previous outcome studies involving CBT or other behavioral therapies. These issues are: (a) the extent to which the CBT conditions produce outcomes that are superior to those produced by a credible attention-placebo condition that adequately controls for the non-specific effects of CBT; (b) identification of baseline participant characteristics, psychosocial variables, and extra-intestinal medical problems that may predict or moderate participant outcomes; (c) identification of cognitive and psychosocial variables that may mediate the outcomes produced by CBT interventions; (d) determining the cost-effectiveness of MC-CBT relative to those produced by S-CBT and attention-placebo control conditions, and e) clarifying the long-term durability of treatment effects.

8.1 Cognitive Behavioral Therapy

Cognitive behavioral therapy (CBT) is a time-limited, highly structured, problemfocused, and prescriptive therapy based on two central underlying assumptions:

- 1) Symptoms are acquired (learned) and reflect specific skills deficits in domains of cognitive and behavioral functioning
- 2) Teaching and rehearsing skills for modifying maladaptive behaviors and thinking patterns can remediate these deficits which, in turn, relieves symptoms.

Specific technical components of CBT protocols typically include:

- Information about stress and its relationship to IBS
 - Self-monitoring of antecedent and consequent events associated with IBS
- Problem solving strategies around stressors that aggravate symptom flare-ups
- Muscle relaxation exercises for cultivating lower physiological arousal and increased sense of mastery over symptoms
- Cognitive restructuring for modifying faulty threat appraisals that underlie physiological and emotional reactivity.

These techniques administered either singly (e.g. cognitive therapy techniques alone) or in combination with other interventions have been featured in 24 randomized clinical trials (RCTs) between 1985 and 2005. The first generation of CBT trials suffered from many methodological flaws. However, as the quality of trials have improved ⁵⁰, a more positive picture of CBT's therapeutic value emerges. In comparison with passive control conditions (e.g. waiting list, no-treatment conditions), CBT generally yields broad improvements in key GI symptoms (pain, bowel dysfunction), quality of life ⁴³, and psychological distress ⁵⁰. Less impressive, albeit statistically significant, results have emerged from the few trials ^{5, 51} that have pitted CBT against an active control (attention placebo) condition that controls for nonspecific therapy effects. These data underscore the importance of adding an attention placebo arm to determine whether CBT's effects are due to particular techniques specified by cognitive behavioral theory (i.e. social learning theory ⁵²) or to nonspecific therapy effects.

CBT has practical limitations restricting its clinical utility. Assuming an hourly charge per 50-minute session of \$90⁵³, a 12-week regimen of individual CBT [5] costs \$1,090. The average wholesale price of a 12-week regimen ⁵ of desipramine, [one of the more efficacious pharmacological agents ⁵], is \$221.76 per participant ⁵⁴. Beyond cost, logistical problems add to CBT's utility problems. Access to CBT is currently restricted by its time intensiveness (median treatment hours = 16 hours ⁵⁵), high level of demand and limited availability of adequately trained therapists ⁵⁶, especially in geographical areas not served by the 5 academic medical centers (US) which deliver CBT for IBS. Clearly, CBT suffers from a very significant technology transfer problem. As the "second generation" of IBS treatments emerges, it is increasingly clear that efficacy demonstration is a necessary but not sufficient condition of treatment viability. An unmet need exists for a brief form of CBT that is less costly, time intensive and more transportable, yet retains the clinical efficacy of the "gold standard" CBT delivered in routine office settings.

One strategy for tackling high treatment delivery costs involves decreasing therapist contact time through the use of primarily self-administered or "home-based" treatments. A self-administered version of CBT could (1) increase the numbers and types of symptomatic people who attain relief from IBS symptoms at relatively low cost and (2) help conserve and allocate scarce health care resources to those participants who require more intensive, clinic-based care. If self-administered CBT is found to be effective, this line of research would represent a major advance in the treatment of this common, often intractable GI disease.

8.2 Minimal-Contact CBT

In a minimal-contact (MC) treatment (e.g. Holroyd ⁵⁷), self-management skills are introduced in periodic (e.g. monthly) clinic sessions but most of what is taught in clinicbased CBT is learned at home using self-study materials developed by the PI. As a result, MC-CBT requires only four clinic sessions rather than the 10-20 weekly sessions featured in the literature. Potential advantages of an MC-CBT approach include: compatibility with the number (six) of sessions most psychotherapy participants attend⁵⁸; greater participant involvement; a reduction in participant costs (direct and opportunity); expanded availability of services; lower stigma; easier scheduling and penetration into underserved areas; and more rapid integration into routine clinical settings participant to yearly HMO limits on outpatient counseling visits. Research exploring the monetary benefit of limited contact treatments in general indicates that the cost effectiveness index of limited contact treatments is more than five times larger than that of clinic-based therapies ⁵⁹. In a health care culture emphasizing a stepped care approach, an MC-CBT treatment may represent a logical first step intervention for individuals who require more than advice, reassurance, or simple lifestyle changes, but a less complex, restrictive, and costly option than specialty care settings typically provide. Potential disadvantages of an MC-CBT approach include greater investment of time, effort, and motivation for the participant at home, and fewer opportunities for corrective feedback. Research that has directly pitted MC-CBT against S-CBT for behavioral medicine problems shows that MC-CBT generally perform at least as well as more time- and labor-intensive versions on primary clinical endpoints 59-60.

These findings provide a data-based rationale for performing tests of the feasibility of a brief CBT for IBS.

- Implementing the interventions in a systematic and standardized fashion consistent with the study protocol
- Collecting high quality data according to the study protocol
- Making provisions to ensure the safety of trial participants
- Collaborating in design and monitoring of the study, including regular attendance at Steering Committee meetings
- Collaborating in the analysis and dissemination of study results

Health Economics Center

The health economics center will be led by [name], Director of the Behavioral Health Economics Program at RTI. RTI International is a nonprofit research organization headquartered in Research Triangle Park, NC. [name] will be responsible for designing and performing the economic analysis which will include a cost analysis of the IBS intervention, and cost-effectiveness and cost-benefit analyses as appropriate. RTI will contribute to the production of reports, publications, presentations and other needs related to the economic analysis as well as developing publications and presentations of the economic findings. RTI also will interact with the Steering Committee, Executive Committee, Data Coordinating Center, and the Data and Safety Monitoring Board as needed on all procedures involving the assessment of economic variables as well as economic data quality and collection, and the economic analyses.

Data Coordinating Center (DCC)

[name] of Frontier Science is the DCC's lead investigator for the project. He will supervise the DCC's operations and will work with study statisticians and data managers to present reports to the DSMB. He will direct and actively participate in preparations of DSMB reports and supervise preparation of other reports. The DCC will take a leadership role in the study's design and scientific conduct. Communication, cooperation, and frequent interaction with investigators are essential ingredients in executing DCC responsibilities. Accordingly, the DCC's responsibilities involve most aspects of the study and include: working with Project PI to develop and refine trial architecture and design study forms; establishing and maintaining data-collection procedures and documenting them in the Manual of Operations; implementing and operating the randomization system; develop data-management and quality assurance procedures in accordance with the final protocol and data-collection procedures; formulation of a study monitoring plan along with the statisticians, producing and

distributing reports, including enrollment, follow-up, protocol adherence, and data quality; analyzing study data for reports, publications, presentations and other needs; and assisting in writing publications and presentations.

The National Institute of Diabetes and Digestive and Kidney Diseases

IBSOS is funded through a cooperative agreement (U01) with the National Institute of Diabetes and Digestive and Kidney Diseases (NIDDK) of the National Institutes of Health (NIH). Details of the relationship between the NIDDK and the IBSOS are included in the "Terms and Conditions for Large Scale Research Project Applications."

APPENDIX 4: Eligibility Criteria

Inclusion Criteria
Gender: male or female
Ages 18-70 years (inclusive)
All ethnic groups
Meet Rome III criteria for IBS
 Moderate to severe IBS symptoms (symptom frequency ≥ 2 days/wk)
Ability to understand and provide informed consent
• With the exception of antibiotics, participant is willing to remain on a stable dose throughout the 4-week pretreatment baseline period prior to randomization
 Participant either not taking medications or if taking medications willing to suspend starting any new medications during the initial 4-week pre- treatment baseline period
A minimum 6 th grade reading level based on the Wide Range Achievement Test (WRAT 4) if necessary
• Participant is willing to be randomized to CBT or Support/Education to which s/he has been assigned and to adhere to protocol requirements
 Participant is willing to attend regularly scheduled therapy sessions during active phase of the trial
 Participant is willing to be contacted and scheduled for follow-up assessments at week 12 and 3, 6, 9, and 12 months after the conclusion of acute treatment phase
 Participant is able to a maintain daily symptom diary and complete questionnaires through treatment and at regularly scheduled follow ups
Participant has access to a telephone
Participant is willing and able to provide adequate information for locator purposes

	Exclusion Criteria
•	Evidence of current structural or biochemical abnormalities or medication use that better explain the participant's IBS symptoms (e.g. IBD)
•	Evidence of a current infection or infection of any type within the 2 weeks prior to the study gastroenterologists' evaluation which would obscure the presentation of IBS symptoms. In such cases the baseline can be delayed until 2 weeks after complete recovery
•	Participant has received antibiotics (e.g. rifaximan and/or neomycin) specifically targeted to treat IBS symptoms. In this instance, eligibility will be suspended for 12 weeks from the initial date the antibiotic was consumed
•	Participant has undergone previous abdominal surgery that would have caused significant alteration of the anatomy/physiology of the digestive/GI tract, which adequately explains GI symptoms
•	Participant has been diagnosed and/or treated for malignancy in the past 5 years with exception of localized basal or squamous cell carcinomas of the skin
•	Participant has an unstable extraintestinal medical condition whose immediate or foreseeable treatment needs (e.g. hospitalization, conflicting physician visits) would realistically interfere with study demands (e.g. consistent attendance at treatment sessions and/or ability to participate in telephone interventions) or may affect the interpretation of clinical efficacy data
•	Participant has a major psychiatric disorder, which in the opinion of the senior clinical staff may impede conduct of the clinical trial. These disorders include but are not limited to major depression with a high risk of suicidal behavior (i.e. intent or plan), alcohol or substance abuse/dependence within the past year, a lifetime history of schizophrenia or schizoaffective disorder or gross cognitive impairments
•	Participant has other conditions which in the opinion of the senior clinical staff would influence negatively the conduct of the clinical trial
•	Participant is currently receiving targeted psychotherapy for IBS and is unwilling or unable to discontinue his/her treatment for the acute treatment phase of this study
•	Participant is unable to complete all scheduled screening visits
•	Participant is inaccessible for interventions and/or follow-up evaluations

APPENDIX 5: Adverse Event Reporting

Completing the Adverse Event Case Report Form (CRF)

- Each adverse event must be reported using the Adverse Event (AE) CRF. If necessary, multiple AE CRF forms may be used for participants.
- After completing the header fields, the clinician should write a brief description of the event on the AE CRF and use the standard definitions provided to indicate:
 - (a) the maximum severity of the AE
 - (b) the current status of the AE
 - (c) date of onset of the AE and, if AE has been resolved, date of resolution
 - (d) whether the AE was expected or unexpected the likelihood that the AE is related to the study treatment intervention.

These ratings are described in detail below.

If a participant did not experience an AE at the end of his/her study period (including follow-up), the clinician will indicate this on the AE CRF. In this case, the clinician will not fill out any other fields on the AE CRF except for the header fields, the Source Document Language field, and Form Completion Status field (filled in as 'Form Completed as Required'). There should be at least one AE CRF completed for each participant, even if a participant did not experience an adverse event during the course of the protocol.

AE Severity Rating

The clinician will rate the severity of each AE using a four-category scale. These categories are defined below. This rating should represent the maximum severity of the adverse event. For example, a participant may report multiple headache events over a short period of time or a prolonged period of chest pain that may vary in intensity. The clinician should provide a rating of the most severe episode of headache or a rating of the chest pain at its maximum severity. The numerical rating of the appropriate category should be recorded in the box marked "Severity."

- 1. Mild: Does not interfere with participant's usual function
- 2. Moderate: Interferes to some extent with participant's usual function
- 3. Severe: Interferes significantly with participant's usual function
- 4. Life-Threatening: Poses a significant threat to the life or functioning of the participant

It should be noted that judgments of AE severity should be independent of judgments regarding whether or not an AE is considered "serious." The term "severe" is typically used to describe the intensity (severity) of an event (as in mild, moderate, or severe pain); the event itself may be of regarded as medically benign (such as severe migraine

headache). This use of "severe" is not the same as "serious," the latter of which is based on participant/event outcome or action criteria usually associated with events that pose a threat to the participant's life or vital functions. Seriousness (not severity) serves as a guide for defining regulatory reporting obligations.

Adverse Event Current Status

The clinician will indicate the current status of the AE at the time of the report using a four-category scale. These categories are described below. The numerical rating of the appropriate category should be recorded in the box marked "Status." In addition, the recorder should indicate the date of the onset of the AE in the boxes provided on the AE CRF.

- 1. New: This report represents the first occurrence of the adverse event
- 2. **Resolved**: The event is no longer ongoing although there still may be lasting problems or complications. If event is resolved, please record the Date and Time of Resolution in the boxes provided on the AE CRF.
- 3. New and Resolved In Same Interval: The AE meets criteria for both New and Resolved AE.
- 4. **Ongoing**: The AE has not been resolved at the time of report.

The Expected or Unexpected Nature of the AE

The clinician will check the appropriate box to indicate whether the AE is expected or unexpected based on the following criteria:

- Unexpected Adverse Event: An adverse event that occurs during the research protocol in which the nature, severity, or frequency of the event is not consistent with either:
 - a. the known or foreseeable risk of adverse events associated with the procedures involved in the research that are described in (a) the protocolrelated documents, such as the IRB-approved research protocol, any applicable investigator brochure, or the current IRB-approved informed consent document, and (b) other relevant sources of information; or
 - b. the expected natural progression of the underlying disease, disorder, or condition of the participants(s) experiencing the adverse event and the participant's predisposing risk factor profile for the adverse event.
- Expected Adverse Event: Any event that does not meet the definition of unexpected adverse event.

Adverse Event Related to Protocol Treatment

The clinician will rate the likelihood that the adverse event was caused by the procedures involved in the research using the following categories and definitions:

- Reasonable Possibility: There is a reasonable possibility that the adverse event, incident, experience or outcome may have been caused by the procedures involved in the research. A *reasonable possibility* is defined as more likely than not the event is causally and consequentially related to the research procedures or, in other words, there is a strong (>50%) likelihood of the event having been caused by the procedures involved in the research
- Not Reasonable Possibility: There is not a reasonable possibility that the adverse event may have been caused by study participation.

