3.4 Secondary Efficacy Endpoints

Secondary efficacy endpoints include the following:

- Adequate relief of abdominal pain two weeks after the end of treatment phase and at quarterly intervals through 12 months
- Adequate relief of bowel problems two weeks after the end of treatment phase and at quarterly intervals through 12 months
- Change from pre-treatment baseline of lower GI function (i.e. stool frequency; stool consistency; severity of urgency, bloating and straining) to post-treatment, and at quarterly follow-ups
- Change from pre-treatment baseline in ratings of (a) severity of abdominal pain/discomfort and (b) global severity of IBS symptoms to post treatment and at quarterly follow-ups
- Change from pre-treatment baseline in indices of health related quality of life to post treatment, and at quarterly follow-ups
- The percent of participants who describe themselves as satisfied with assigned treatment at 2-week follow-up using the Client Satisfaction Scale.
- Change from pre-treatment baseline in psychological well-being (e.g. overall mental well-being and discrete emotional problems such as anxiety, depression, somatization) to post treatment, and at quarterly follow-ups

- Change from pre-treatment baseline in health care use to post-treatment, and at quarterly follow-ups
- Gains in estimated quality adjusted life years (QALYs) from pre- to post-treatment
- Change from pre-treatment baseline in extraintestinal symptoms to post-treatment, and at quarterly follow-ups
- The percent of participants responding positively to treatment as measured by the adequate relief of pain and adequate relief of bowel symptoms
- The percent of participants who report adequate relief, improved symptoms, and clinically significant reduction of IBS symptoms by week four (rapid response)
- Safety as measured by the occurrence of adverse events

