Examples of noncompliance arise if a participant fails to attend two consecutive MC-CBT or S-CBT sessions, or three consecutive EDU sessions without a reason deemed appropriate by his or her therapist and site PI. Non-compliance with homework is not regarded as an acceptable basis for withdrawal.

4. **Administrative error** — Participants who do not meet all study inclusion or exclusion criteria may enter the study in error.

For example, a participant who does not disclose concurrent targeted psychotherapy for IBS or the presence of a medical condition that makes it unsafe or impractical for the participant to continue may be withdrawn at the PI's discretion. These participants may be replaced because they would not have satisfied eligibility criteria had the participant fully disclosed information regarding health status at the time eligibility was determined.

			Page 1 of 2
DATA COLLECTI	ON FORMS S	CHEDULE	00-00-00
ST	UDY IBSOS1 BOOK 1		
NOTE: The columns are marked with an "X" to indicate data and evaluation	ns required at each visit.	PRE-TREATMENT BASELINE	PREMATURE DISCONTINUATION
eData/HAND-ENTERED FORMS	Frontier Form #/ Reference		
IBS0S1 Study Participant Intake Form	QLW01	×	
IBS - Symptom Severity Scale	QLW03	×	
TEV- BL	QLW10	×	
IBSOS Comorbid Disease Form	QLW13	×	
MD Rating - Baseline	QLW15	×	
Concomitant Medications/Supplements and Non-Drug Therapies	CMW1	×	
IBS Module (IBS-PRO)	QLW14	×	
IBSOS1 Study Participant Economic Form	QLW06	×	
FMBS	QLW12	×	
Euroqol EQ- 5D	QLW02	×	
Adverse Events	IBS0021		×
Off Study / Drop Out	IBS1601		×
Missed Visit	ST0010		
Death Form	SP1411		
FLIPS FORMS	Frontier Form #/ Reference		
IBS - LOC	ibsloc	×	
IBS SE Questionnaire	ibsse	×	
bSS	bss	×	
PCSQ-2 Item	pcsq2	×	
IBS-QOL Instrument	ibsqol	X	
McGill - SF	mcgsf	×	
The SF - 12 Health Survey	sf12	×	
Restorative Activities	restact	×	
SOMS-7	soms7	×	
ASI	asi	×	
NSI	vsi	X	
Continued on page 2.			

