APPENDIX 7: Data Collection Schedule

			Page 2 of 2
DATA COLLECTIC	DN FORMS S JDY IBSOS1 BOOK 1	CHEDULE	00-00-00
NOTE: The columns are marked with an "X" to indicate data and evaluation:	s required at each visit.	PRE-TREATMENT BASELINE	PREMATURE DISCONTINUATION
FLIPS FORMS (continued)	Frontier Form #/ Reference		
DIS	dis	×	
PSWQ-A	pswda	×	
ER	er	×	
BDI-II	bdiii	×	
BSI-18	bsi18	×	
STAI-SF	staisf	×	
K-ESS	kess	×	
ISEL-12	isel12	×	
IIP-32	iip32	×	
NIS	nis	×	
TSRQ (A)	tsrqa	×	
Non-Form Evaluation (Exported to Database)			
MINI International Neuropsychiatric Exam Plus	mini	×	
Site-Use Only forms (Not Entered into Database)			
Health Care Coverage f Form		×	
Locator Form		×	

										_	Page 1	of 2
DATA COLLEC	TION FOI	RMS	0)	SCH	Ш		щ				00-00	00-(
STUC	 0Y IBSOS1 - B	OOK 2	~									
NOTE: The columns are marked with an "X" to indicate data and evaluations required at each visit.		Clinic Visit 1	2	OBT and Tel. /isit 1		leation Slinic Isit 2	al Su v	pport T Tel. isit 2	reatme Clinic Visit 3	2 건	inic sit 4	
					5 C	:BT - T	reatm	ent			•	REM.
	Veeks →	1	2	3	4	5	6	7	8	6	10 [ISC.
eData/ HAND-ENTERED FORMS	Frontier Form #/ Reference											
IBS - Symptom Severity Scale	QLW03				_	×				-		×
IBSOS Comorbid Disease Form	QLW13											×
Concomitant Medications/Supplements and Non-Drug Therapies	CMW1	×	×	×	×	×	×	×	×	×	×	×
IBS Module (IBS-PRO)	QLW14											×
IBSOS1 Study Participant Economic Form	QLW06											×
FMBS	QLW12											×
Euroqol EQ-5D	QLW02											×
IBSOS Daily Diary	LGW1	×	×	×	×	×	×	×	×	×	×	×
IBSOS1 Study Participant Follow Up Form	QLW17											×
LEV-FU	QLW11											×
MD Rating- Follow Up	QLW16											×
Adverse Events	IBS0021											×
Off Study / Drop Out	IBS1601											×
Missed Visit	ST0010											
Premature Discontinuation of Study Treatment	IBS4000											
Death Form	SP1411											
FLIPS FORMS	Frontier Form #/ Reference											
BS - LOC	ibsloc	×		×		×			×			×
IBS SE Questionnaire	ibsse	×		×		×			×			×
bSS	ssd	×		×		×			×			×
PCSQ-2 Item	pcsq2	×		×		×			×			×
IBS-QOL Instrument	ibsqol		_									×
McGill - SF	mcgsf		_									×
The SF - 12 Health Survey	sf12		-		_		_			_		×
Restorative Activities	restact		_		_		_	_		_		×
Continued on page 2.												

										Pag	e 2 of 2	
DATA COLLEC	TION FO	RMS 300K 2	S	CH	B	Ч	ш			00	00-00-	
NOTE: The columns are marked with an "X" to indicate data and evaluations required at each visit.		Clinic	v	BT and Tel.	Cli	ationa	Tel.	ort Treatm Clinic	Jent	Clinic		1

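### Appendix 7 requires the Adverse Events form only at premature discontinuation; this does not agree with Appendix 5 and leaves no AE enquiry common to the three arms

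*Protocol*

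**What the plan says.** Protocol 3.4 lists among the secondary endpoints "Safety as measured by the occurrence of adverse events".

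Appendix 5 sets a general duty: "Each adverse event must be reported using the Adverse Event (AE) CRF". It adds "There should be at least one AE CRF completed for each participant, even if a participant did not experience an adverse event", and places the negative entry at the close of participation: "If a participant did not experience an AE at the end of his/her study period (including follow-up), the clinician will indicate this".

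Appendix 7 explains that an X marks a form required at a visit. In the row "Adverse Events" (form IBS0021) each of Books 1, 2 and 3 has a single X, always under premature discontinuation. The pre-treatment baseline, treatment weeks 1 to 10 and the five follow-up visits have none.

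Appendix 9 (protocol review and study monitoring) has the safety officer judge whether AE frequency during treatment departs sharply from baseline, and calls the trial unmasked.

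**The concern.** A form required of every participant has no scheduled visit for anyone who stays in the trial. Appendix 5 expects a completer without an AE to have a negative entry at the end of follow-up, but the month 12 column of Book 3 does not call for the form. The baseline-to-treatment comparison in Appendix 9 has no scheduled AE form at either end.

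Two separate consequences follow.

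- **Contact count.** If events are recorded only when a participant mentions them, an arm with more sessions offers more occasions to do so. S-CBT could then show more AEs than MC-CBT or ACC with the same true incidence, and the safety officer and the DSMB would see the same counts.
- **Completion status.** A participant who drops out has an AE form at discontinuation. A completer without an AE has one at the end of the study period. The timing of the form therefore depends on whether the participant stayed.

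**Working it through.** **1. The schedule row against other rows (Appendix 7).**

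| Form | Book 1 baseline | Book 2 weeks 1–10 | Book 3 follow-ups | Premature discontinuation |
|---|---|---|---|---|
| Adverse Events | none | none | none | X in all three books |
| Concomitant Medications | X | X every week | X at all five | X in Books 2 and 3 |
| Off Study / Drop Out | none | none | none | X in all three books |
| Death, Missed Visit | none | none | none | none |

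Where regular enquiry was meant, the schedule marks it. Forms triggered purely by an event carry no X. The AE form follows the Off Study pattern.

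**2. Appendix 5 against Appendix 7.** Appendix 5 requires an AE form for each participant, completers included. Appendix 7 requires it of no completer at any visit. Appendix 5 also has a status category for an event that begins and resolves within one interval, which presupposes reporting intervals that the schedule does not set.

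**3. Treatment contacts (6.1 to 6.3).** S-CBT: 10 sessions. MC-CBT: 4 visits + 2 calls = 6. ACC: 4 sessions + 2 calls = 6. The ratio is 10/6 = 1.67. All arms share five follow-up assessments (Appendix 8), giving 10 + 5 = 15 against 6 + 5 = 11.

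**4. Illustration of size.** The protocol states no figure to reproduce. Assume equal true incidence, unprompted reporting, and a chance q per contact that an event is mentioned and recorded. Capture over k contacts is 1 − (1 − q)^k. The values of q are assumptions.

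| q | k = 10 vs 6 | Ratio | k = 15 vs 11 | Ratio |
|---|---|---|---|---|
| 0.05 | 0.401 vs 0.265 | 1.51 | 0.537 vs 0.431 | 1.25 |
| 0.10 | 0.651 vs 0.469 | 1.39 | 0.794 vs 0.686 | 1.16 |
| 0.20 | 0.893 vs 0.738 | 1.21 | 0.965 vs 0.914 | 1.06 |
| limit q → 0 | – | 10/6 = 1.67 | – | 15/11 = 1.36 |

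In absolute terms, with an assumed true AE risk of 20% and q = 0.10, the recorded risk is 0.20 × 0.651 = 13.0% against 0.20 × 0.469 = 9.4% on treatment contacts only. With the five follow-ups it is 15.9% against 13.7%.

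**5. Where a common enquiry fits.** Book 2 places the MC-CBT and ACC visits and calls at weeks 1, 3, 5, 7, 8 and 10. Appendix 8 names the same weeks for recording concomitant medications. S-CBT meets every week, so all arms have a contact at these six points.

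**The case against.** A reader might infer that AEs are actively sought in dropouts and merely volunteered by completers, so that S-CBT will appear 20 to 65% worse. The document does not support this.

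- It never says that AEs are asked about at dropout; an X says only that a form is required. Nor does it say that completers' events rest on volunteered reports. Appendix 5 requires a form from them too, and the X at discontinuation may simply be the same close-out form for someone leaving early.
- Missing marks do not prove missing collection. Section 7.2 refers to a manual of operations, not at hand, that may contain a prompt. Appendix 9 has investigators monitor safety continually, and the interval wording in Appendix 5 suggests that repeated reports were expected.
- The 20 to 65% range needs an assumed reporting chance and ignores the five follow-ups that all arms share, offered whether or not therapy was completed. Including them brings the ratio down to 1.06 to 1.25 over the same values of q.
- Dropout timing and contact count are different mechanisms. No differential dropout is shown, and the contact count cannot affect MC-CBT versus ACC.
- Safety is in neither Hypothesis 1 nor the analysis section, and Appendix 9 expects no particular risk from the treatments.

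All of this stands as a limit on the size and certainty of any bias. It does not reconcile Appendix 5 with Appendix 7, and it does not supply the baseline and treatment AE data that Appendix 9 relies on.

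**Conclusion.** The point holds as an inconsistency with a conditional consequence. Appendix 7 schedules the AE form only at premature discontinuation, Appendix 5 requires it of everyone, and Appendix 9 assumes a comparison that the schedule does not feed. No AE enquiry common to the arms is fixed for a listed endpoint.

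AE capture could favour or penalise an arm only if reporting is unprompted, and then only between S-CBT and the other two. Under the assumed q of 0.05 to 0.20 the ratio is about 1.2 to 1.5 on treatment contacts alone and about 1.06 to 1.25 with the shared follow-ups. The true size cannot be obtained from the protocol. The difference in form timing between dropouts and completers without an AE is a separate and unquantified weakness. The matter should be corrected because the remedy is cheap, not because bias has been shown.

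**What to change.** Reconcile Appendices 5 and 7:

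- Mark IBS0021 at baseline, at weeks 1, 3, 5, 7, 8 and 10, and at week 12 and months 3, 6, 9 and 12.
- At each point ask one standard question covering the time since the last enquiry. The month 12 mark also gives the negative entry in Appendix 5 a scheduled place.
- Keep the form at premature discontinuation.
- Base between-arm AE comparisons on these common enquiries, and list separately the AEs volunteered only at the other four S-CBT sessions (10 − 6 = 4).

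Every enquiry falls at a contact that already takes place. The cost is a few more forms to enter and a higher recorded AE count in all arms. A common question equalises the occasions for reporting; it cannot remove every effect of closer therapist contact in an unmasked trial.
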